## 5.9 Protocol Deviations

---

AbbVie does not allow intentional/prospective deviations from the protocol except when necessary to eliminate an immediate hazard to study subjects. The investigator is responsible for complying with all protocol requirements, written instructions, and applicable laws regarding protocol deviations. If a protocol deviation occurs (or is identified, including those that may be due to the COVID-19 pandemic), the investigator is responsible for notifying IEC/IRB, regulatory authorities (as applicable), and AbbVie.

In Japan, the investigator will record all protocol deviations in the appropriate medical records at the site.

## 6 SAFETY CONSIDERATIONS

### 6.1 Complaints and Adverse Events

---

#### Complaints

A complaint is any written, electronic, or oral communication that alleges deficiencies related to the physical characteristics, identity, quality, purity, potency, durability, reliability, safety, effectiveness, or performance of a product/device. Complaints associated with any component of this investigational product must be reported to AbbVie.

#### Product Complaint

A product complaint is any complaint related to the drug component of the product.

For a product this may include, but is not limited to, damaged/broken product or packaging, product appearance whose color/markings do not match the labeling, labeling discrepancies/inadequacies in the labeling/instructions (e.g., printing illegible), missing components/product, device damage or not working properly, or packaging issues.

Product complaints concerning the investigational product and/or device must be reported to AbbVie within 24 hours of the study site's knowledge of the event. Product complaints occurring during the study will be followed up to a satisfactory conclusion.

#### Medical Complaints/Adverse Events and Serious Adverse Events

An AE is defined as any untoward medical occurrence in a subject or clinical investigation subject administered a pharmaceutical product and which does not necessarily have a causal relationship with this treatment. An AE can therefore be any unfavorable and unintended sign (including an abnormal laboratory finding), symptom, or disease temporally associated with the use of a medicinal (investigational) product, whether or not the event is considered causally related to the use of the product.

Such an event can result from use of the drug as stipulated in the protocol or labeling, as well as from "special situations" such as accidental or intentional overdose, medication error, occupational or accidental exposure, off-label use, drug abuse, drug misuse, or drug withdrawal, all which must be reported whether associated with an AE or not. Any worsening of a pre-existing condition or illness is considered an AE. Worsening in severity of a reported AE should be reported as a new AE. Laboratory abnormalities and changes in vital signs are considered to be AEs only if they result in discontinuation from the study, necessitate therapeutic medical intervention, meets protocol-specific criteria (see Section 6.2 regarding toxicity management), and/or if the investigator considers them to be AEs.

The investigators will monitor each subject for clinical and laboratory evidence of AEs on a routine basis throughout the study. All AEs will be followed to a satisfactory conclusion.

An elective surgery/procedure scheduled to occur during a study will not be considered an AE if the surgery/procedure is being performed for a pre-existing condition and/or the surgery/procedure has been pre-planned prior to study entry. However, if the pre-existing condition deteriorates unexpectedly

during the study (e.g., surgery performed earlier than planned), then the deterioration of the condition for which the elective surgery/procedure is being done will be considered an AE.

If an AE, whether associated with study drug or not, meets any of the following criteria, it is to be reported to AbbVie clinical pharmacovigilance or contract research organization (as appropriate) as an SAE within 24 hours of the site being made aware of the SAE (refer to Section 4.3 of the operations manual for reporting details and contact information):

Death of Subject	An event that results in the death of a subject.
Life-Threatening	An event that, in the opinion of the investigator, would have resulted in immediate fatality if medical intervention had not been taken. This does not include an event that would have been fatal if it had occurred in a more severe form.
Hospitalization or Prolongation of Hospitalization	An event that results in an admission to the hospital for any length of time or prolongs the subject's hospital stay. This does not include an emergency room visit or admission to an outpatient facility.
Congenital Anomaly	An anomaly detected at or after birth, or any anomaly that results in fetal loss.
Persistent or Significant Disability/Incapacity	An event that results in a condition that substantially interferes with the activities of daily living (ADL) of a study subject. Disability is not intended to include experiences of relatively minor medical significance such as headache, nausea, vomiting, diarrhea, influenza, and accidental trauma (e.g., sprained ankle).
Important Medical Event Requiring Medical or Surgical Intervention to Prevent Serious Outcome	An important medical event that may not be immediately life-threatening or result in death or hospitalization, but based on medical judgment may jeopardize the subject and may require medical or surgical intervention to prevent any of the outcomes listed above (i.e., death of subject, life threatening, hospitalization, prolongation of hospitalization, congenital anomaly, or persistent or significant disability/incapacity). Additionally, any elective or spontaneous abortion or stillbirth is considered an important medical event. Examples of such events include allergic bronchospasm requiring intensive treatment in an emergency room or at home, blood dyscrasias or convulsions that do not result in inpatient hospitalization, or the development of drug dependency or drug abuse.

All AEs reported from the time of study drug administration until 30 days or 5 half-lives, whichever is longer, after discontinuation of study drug administration will be collected, whether solicited or spontaneously reported by the subject. In addition, study procedure-related serious and nonserious AEs will be collected from the time the subject signs the study-specific informed consent.

The following definitions will be used for Serious Adverse Reactions (SARs) and Suspected Unexpected Serious Adverse Reactions (SUSARs):

SAR	Defined as all noxious and unintended responses to an Investigational Medicinal Product (IMP) related to any dose administered that result in an SAE as defined above.
SUSAR	Refers to individual SAE case reports from clinical trials where a causal relationship between the SAE and the IMP was suspected by either the sponsor or the investigator, is unexpected (not listed in the applicable Reference Safety Information), and meets one of the above serious criteria.

AbbVie will be responsible for SUSAR reporting for the Investigational Medicinal Product (IMP) in accordance with global and local requirements.

AEs will be monitored throughout the study to identify any of special interest that may indicate a trend or risk to subjects.

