## Adverse Event Severity and Relationship to Study Drug

The investigator will rate the severity of each AE according to the NCI CTCAE version 5.0, which can be accessed at: [http://ctep.cancer.gov/protocolDevelopment/electronic\\_applications](http://ctep.cancer.gov/protocolDevelopment/electronic_applications).

If no grading criteria are provided for the reported event, then the event should be graded as follows:

**Mild (Grade 1)** Asymptomatic or mild symptoms; clinical or diagnostic observations only; intervention not indicated

**Moderate (Grade 2)** Minimal, local, or noninvasive intervention indicated; limiting age-appropriate instrumental ADL (instrumental ADL refer to preparing meals, shopping for groceries or clothes, using the telephone, managing money, etc.)

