**Management of Select Laboratory Abnormalities:** For any given laboratory abnormality, the investigator should assess the subject, apply the standard of care for medical evaluation and treatment following any local guidelines. Specific toxicity management guidelines for abnormal laboratory values are described in [Table 3](#) and may require a supplemental eCRF to be completed. For subjects with ongoing laboratory abnormalities which require data entry into an eCRF, an additional eCRF related to subsequent laboratory abnormalities is only required if the subject has relevant changes in history (e.g., new onset signs or symptoms) or laboratory values which have returned to normal reference range or its Baseline value followed by subsequent laboratory abnormalities meeting toxicity guidelines (considered a new event). All abnormal laboratory tests that are considered clinically significant by the investigator will be followed to a satisfactory resolution. If a repeat test is required per [Table 3](#), the repeat testing is to occur as soon as possible. Further, repeat testing may be performed at a local laboratory if the subject is unable to use the central laboratory.

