10.2 Adverse Events

Adverse events (AEs) will be summarized and presented using primary MedDRA System Organ Classes (SOCs) and preferred terms (PTs) according to the version of the MedDRA coding dictionary used for the study at the time of database lock. The actual version of the MedDRA coding dictionary used will be noted in the AE tables and in the clinical study report. Specific adverse events will be counted once for each subject for calculating percentages, unless stated otherwise. In addition, if the same adverse event occurs multiple times within a subject, the highest severity and level of relationship to investigational product will be reported.

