10.2.1 Treatment-Emergent Adverse Events

For Period 1, treatment-emergent adverse events (TEAEs) are defined as any adverse events that begin or worsen in severity after initiation of study drug through 30 days following the last dose of study drug in Period 1 or prior to first dose in Period 2, whichever is earlier. For Period 2, TEAEs are defined as any adverse events that begin or worsen in severity after initiation of study drug in Period 2 through 30 days following the last dose of study drug in Period 2. A TEAE during the administration of upadacitinib (i.e., among the ALL_UPA Population) is defined as any AE with an onset date on or after the first dose of upadacitinib and within 30 days after the last dose of upadacitinib. Events where the onset date is the same as the study drug start date are assumed to be treatment emergent.

All TEAEs will be summarized overall, as well as by primary MedDRA SOC and PT. The SOCs will be presented in alphabetical order, and the PTs will be presented in alphabetical order within each SOC. For the Safety_1 and ALL_UPA Populations, the number and percentage of subjects experiencing TEAEs and the number of events per 100 patient-years of exposure will be summarized.

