10.2.2 Adverse Event Overview

An overview of AEs will be presented consisting of the number and percentage of subjects experiencing at least one event for each of the following AE categories for the Safety_1 and ALL_UPA Populations:

- Any TEAE
- Any TEAE related to study drug according to the investigator
- Any severe TEAE (Grade 3 and above according to National Cancer Institute (NCI) Common Terminology Criteria for Adverse Events (CTCAE) version 5)
- Any serious TEAE (SAE)
- Any TEAE leading to discontinuation of study drug
- Any TEAE leading to death
- TEAEs of special interest

- All deaths
- Deaths occurring \leq 30 days after last dose of study drug
- Deaths occurring $>$ 30 days after last dose of study drug.

The overview of number of TEAEs/deaths per 100 patient-years of exposure will also be provided for the above categories for the Safety_1 and ALL_UPA Populations.

TEAEs per 100 patient-years of exposure are defined as the number of TEAEs divided by the total exposure in 100 patient-years. The exposure-adjusted TEAE rate per 100 patient-years is calculated as:

$$100 \times \frac{\text{Number of TEAEs}}{\text{Total Patient Years}}$$

where total patient years is defined as the sum of the study drug duration (defined in Section 6.0) +1 day (not to exceed the start of subsequent period) of all subjects normalized by 365.25, and rounded to 1 decimal place.

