10.2.5 Adverse Events of Special Interest

Treatment emergent Adverse events of special interest (AESI) will be summarized by SOC and PT and will be based on standardized or company MedDRA queries (SMQs or CMQs) or based on adjudication results. The number and percentage of subjects experiencing treatment emergent AESIs and the number of events per 100 patient-years of exposure of the AESI overview table will be summarized for the Safety_1 and ALL_UPA Populations. For ALL_UPA, number of events per 100 patient-years of exposure of the AESI by SOC and PT will be summarized.

Adverse events of special interest are categorized as follows:

- Serious infections
- Opportunistic infection excluding tuberculosis and herpes zoster
- Possible malignancy
- Malignancy
- Non-melanoma skin cancer (NMSC)
- Malignancy excluding NMSC
- Lymphoma
- Hepatic disorder
- Adjudicated gastrointestinal perforation

- Anemia
- Neutropenia
- Lymphopenia
- Herpes zoster
- Renal dysfunction
- Active tuberculosis
- Adjudicated MACE
- Adjudicated VTE

Detailed information about the search criteria is provided in [Appendix B](#).

Tabular listings of adverse events of special interest will be provided.

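### Event rates per 100 patient-years count each worsening of one unresolved adverse event as a further event, because the SAP has no rule joining the records of an episode

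*Protocol*

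**What the plan says.** - **Recording.** Protocol Section 6.1 (Medical Complaints/Adverse Events and Serious Adverse Events): "Worsening in severity of a reported AE should be reported as a new AE". The same section sets the scale: "The investigator will rate the severity of each AE according to the NCI CTCAE version 5.0". That scale has five grades.
- **What qualifies.** SAP Section 10.2.1 defines a TEAE in each period as "any adverse events that begin or worsen in severity after initiation of study drug" for that period. For the ALL_UPA Population it uses onset date alone: "any AE with an onset date on or after the first dose of upadacitinib", up to 30 days after the last dose.
- **The rate.** SAP Section 10.2.2: "TEAEs per 100 patient-years of exposure are defined as the number of TEAEs divided by the total exposure in 100 patient-years".
- **De-duplication.** SAP Section 10.2, repeated in 10.2.3: "Specific adverse events will be counted once for each subject for calculating percentages, unless stated otherwise". The sentence that follows says that, for a repeated event, the highest severity and the strongest relationship are shown.
- **Where the rate is used.** For Safety_1 and ALL_UPA, it appears in the overview (10.2.2), the tables by system organ class and preferred term (10.2.3), SAEs and discontinuations (10.2.4) and AESIs, where the "number of events per 100 patient-years of exposure of the AESI overview table will be summarized" (10.2.5).

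**The concern.** A reader takes events per 100 patient-years to be the frequency with which events occur. Under these rules, an event that starts at Grade 1 and moves to Grade 2 and then Grade 3 without resolving is three records, and all three enter the numerator. A treatment group can therefore show a higher rate because its events change grade more often, not because it has more events. The groups are small, so a few such records move a rate visibly. The rate can also rise while the percentage of subjects reported for the same event stays put, and nothing in the SAP tells the reader why.

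**Working it through.** The plan states no AE count, AE rate or expected number of worsenings, so there is no figure to reproduce. The check follows one episode through the rules and then applies the SAP formula.

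**Step 1: does each record count?**
- Protocol 6.1 makes the Grade 1, Grade 2 and Grade 3 stages of one unresolved course three AE records.
- Under SAP 10.2.1, the first record begins on treatment and the later ones are worsenings on treatment, so all three are period TEAEs. In ALL_UPA, each new record has its own onset date and qualifies on that date.
- SAP 10.2.2 counts TEAEs. The once-per-subject rule is confined to percentages. The highest-severity sentence settles which grade is shown, not how many events are counted.
- Result: three events in the rate and one subject in the percentage.

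**Step 2: Period 1 exposure per group.** Inputs are 40 subjects per group (SAP 2.4), Week 24 on Day 169 (Protocol Appendix D), and full exposure (assumed). For a subject who continues into Period 2, SAP 6.0 gives a duration of 168 days. The extra day in SAP 10.2.2 may not run past the start of the next period, so it adds nothing.

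40 × 168 / 365.25 = 18.4 patient-years

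**Step 3: weight of one record.** 100 / 18.4 = 5.4 events per 100 patient-years. The Grade 1 to 2 to 3 course contributes 300 / 18.4 = 16.3 instead of 5.4.

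**Step 4: a small AESI example.** Three subjects have one course each, and two of the courses worsen once.

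| | Count | Per 100 patient-years |
|---|---|---|
| Episodes | 3 | 300 / 18.4 = 16.3 |
| Records, as the SAP counts | 5 | 500 / 18.4 = 27.2 |
| Subjects | 3 of 40 = 7.5% | not applicable |

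**Step 5: ALL_UPA.** Full exposure is again assumed. A subject on upadacitinib from Baseline contributes 364 + 1 = 365 days, and a placebo switcher 196 + 1 = 197 days.
- 6 mg: 40 × 365 / 365.25 = 40.0 patient-years, so one record adds 2.5.
- 11 mg or 22 mg: (40 × 365 + 20 × 197) / 365.25 = 50.8 patient-years, so one record adds 2.0.

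**Step 6: all-TEAE rate.** If a share w of episodes worsens once, the rate is multiplied by (1 + w). With an assumed one episode per subject in Period 1, the episode rate is 100 × 40 / 18.4 = 217.4. The record rate is 228.3 at w = 5% and 282.6 at w = 30%.

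**Step 7: rate ratio when the true ratio is 1.00.** The reported ratio is (1 + w on upadacitinib) / (1 + w on placebo). The shares are assumptions.

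| Placebo | Upadacitinib | Reported ratio |
|---|---|---|
| any share | same share | 1.00 |
| 15% | 20% | 1.20 / 1.15 = 1.04 |
| 10% | 25% | 1.25 / 1.10 = 1.14 |
| 5% | 30% | 1.30 / 1.05 = 1.24 |

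With the shares reversed, the ratio falls below 1: 1.15 / 1.20 = 0.96 and 1.05 / 1.30 = 0.81.

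**The case against.** The best defence is that the documents agree with one another. The protocol calls a worsening a new AE, the SAP's period definition includes worsening, and the rate counts TEAEs. Event rates are expected to differ from subject percentages, since true recurrences count too. Percentages, summaries by maximum toxicity, AESI listings and laboratory shift tables are also planned, and the SAP specifies no between-group test of safety data. All of this stands, and it limits the harm. It does not tell the reader that the rate counts grade changes as well as occurrences.

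Several stronger readings are tempting, and the documents do not support them.

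- **A conflicting event definition.** Protocol Section 6.2 calls a laboratory abnormality a new event after return to normal or Baseline. That sentence governs when a further supplemental eCRF is needed, and it also allows one after a relevant change in history. It does not define AE counts, so it does not contradict Section 6.1.
- **Every laboratory grade step becomes an AE.** Section 6.1 limits laboratory AEs to those that lead to discontinuation, need intervention, meet protocol-specific criteria or are judged AEs by the investigator. For neutrophils, lymphocytes and total white cells, the Table 3 thresholds (1000, 500 and 2000/µL) coincide with the Grade 3 cut-offs in SAP Appendix C. Lower grades are recorded only by another of those routes.
- **All rates are equally exposed.** If only the worst record is serious or leads to stopping, one SAE or one discontinuation is counted. Serious infections are restricted to SAEs, and MACE, VTE and GI perforation rest on adjudication or medical review. These outputs are little affected.

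The operations manual and eCRF are not among the documents reviewed. A linking rule there cannot be excluded, but SAP 10.2.2 cites none.

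**Conclusion.** The point holds on the text. As the rules stand, one unresolved episode enters the event rates once for each recorded severity level, and the SAP neither joins these records nor says that it counts them separately. At full Period 1 exposure, each extra record adds about 5.4 events per 100 patient-years in a 40-subject group, and shorter exposure would make it more. The effect lies mainly in the all-TEAE, SOC/PT and some non-serious AESI rates.

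A reader might infer that the comparison between doses is biased against upadacitinib. The documents do not establish that. They give no frequency of worsening and no reason to fix its size or direction by dose. Equal shares inflate the rates and leave the ratios alone. The 1.04 to 1.24 range rests wholly on assumed shares that are higher on upadacitinib. The supported conclusion is that the rates are hard to interpret and that a dose comparison could be distorted.

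**What to change.** Add a counting rule to SAP Section 10.2.2 for all tables of events per 100 patient-years:

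- Within each analysis window, count consecutive records of the same preferred term in the same subject as one event when the later record is a worsening of an unresolved earlier one.
- Give the joined event the first treatment-emergent onset in that window, the highest grade, and any seriousness, relationship or discontinuation flag carried by its records.
- Do not join across the first dose of study drug. Procedure-related AEs are collected from consent, and joining could move an on-drug worsening to a pre-dose onset. For placebo switchers, do not join across the first upadacitinib dose.
- In ALL_UPA, do join across the Period 1/Period 2 boundary for subjects on upadacitinib throughout. Otherwise their ongoing episodes are still counted twice.

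Alternatively, keep the record-based rate, label it as such, and show the episode-based rate beside it.

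The cost is a short SAP addition and one derivation step. It should need no new data, assuming that AE start and end dates, grade and coded term are held for each record. The small downside is that worsening no longer adds to the episode rate, but it stays visible in the maximum-toxicity table.

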### Adverse Events of Special Interest

The following AESIs will be monitored during each study:

- Serious infections
- Opportunistic infections (excluding TB and herpes zoster)
- Herpes Zoster
- Active TB
- Adjudicated GI perforations
- Malignancy (all types)
- Anemia
- Neutropenia
- Lymphopenia
- Renal dysfunction
- Hepatic disorders
- Adjudicated cardiovascular events (e.g., major adverse cardiovascular event)
- Adjudicated embolic and thrombotic events (non-cardiac, non-central nervous system)

### Cardiovascular Adjudication Committee

An independent, external committee of physician experts in cardiovascular adjudication will be utilized to assess potential cardiovascular, cerebrovascular, embolic, and thrombotic AEs in a blinded manner as defined by the CAC charter. The CAC charter will be prepared separate from the protocol and will describe the objective, scope, frequency, and triggers for data reviews.

